9.3 Safety measurements

The number and proportion of participants with at least one adverse event (AE), and the total number of AEs, will be tabulated by the treatment arm. AEs will be tabulated by diagnosis, severity and relationship to the intervention.

The number and proportion of participants who are still in hypertension care 6 months after enrolment will be tabulated by the treatment arm. Retention in care will be defined as currently having sufficient BP medicine in possession (taking into account the date of last visit and the amount of medication dispensed), as the primary definition. As a secondary definition, retention will be defined as having seen a health care worker for

hypertension in the past 3 months. Logistic regression will be used to estimate the OR and 95% CI for the effect of each intervention on retention in hypertension care. The model will include terms for treatment arm, clinic and active use of hypertension medication at baseline.

10. Additional exploratory analyses

The effect of each intervention (vs SOC) on mean change from baseline in systolic blood pressure over 12 months will be estimated using a linear mixed model. The response variable will be systolic blood pressure (at 6 and 12 months); the model will include fixed effects for treatment arm, visit, a treatment arm-visit interaction term, randomisation strata (clinic and active use of hypertension medication at enrolment) and baseline systolic blood pressure, and participant as a random effect to account for correlation of repeated measurements within the participant. The inclusion of the interaction term allows the effect of the intervention to differ over time. If the interaction term is not statistically significant at $p < 0.10$, we will drop it from the model and estimate the overall effect of each intervention (vs SOC) on the change in systolic blood pressure during the trial.

The effect of each intervention (vs SOC) on blood pressure control over 12 months will be estimated using random effects logistic regression. The model will include fixed effects for treatment arm, visit, randomisation strata (clinic and active use of hypertension medication at enrolment) and treatment arm-visit interaction term, and random effects for the participant to account for correlation of repeated measurements. If the interaction term is not statistically significant at $p < 0.10$, we will drop it from the model and estimate the overall effect of each intervention on the blood pressure control pressure during the trial.

All participants with outcome data at either follow-up visit will be included in these analyses. Estimates from random effects models are valid under the assumption that the outcome data are missing at random conditional on the observed outcome at the non-missing visits, and other covariates in the model.

For participants with missing outcome data at month 6 or month 12, we may impute blood pressure measurements at those time points, using multiple imputation by

chained equations. Imputation models will contain observed blood pressure measurements, age, sex, BMI, smoking status, use of anti-hypertensive medication, HIV, clinic, treatment group and any covariates that are found to be associated with missingness.

The consistency of the effect of the intervention on the primary outcome will be assessed in the following pre-specified groups, using a statistical test of interaction. Effect estimates and 95% confidence intervals will be presented for each subgroup, plus the interaction p-value.

- Individuals with systolic blood pressure (SBP) ≥ 160 mmHg and those with SBP < 160 mmHg at enrolment.
- Individuals based on self-reported HIV status.
- Men and women
- Individuals aged ≥ 60 years and < 60 years.

References

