Participants in the (CBPM) arm will be given an Omron BP Cuff and a standardized training on its operation and assigned a CBPM from the study teams. The participant will be instructed to take daily BP measurements using their BP cuffs. CBPMs will return to participant homes every 2-4 weeks, or as guided by the clinic nurse, to collect BP measurements and enter them into a data collection system, assess for symptoms, and discuss treatment adherence and lifestyle recommendations. BP readings will be transmitted to the assigned nursing supervisors at each clinic, who will initiate and/or tailor medications and other recommendations with guidance from a standardized clinical decision support algorithm, based on SA DoH hypertension control guidelines. Treatment decisions will be made by the nursing supervisors. Participants will either obtain medication(s) at the pharmacy or, as possible, have them delivered by a CBPM. As with the SOC arm, medications used will include those on the South African Essential Drug list, which are available in the clinic pharmacy (including hydrochlorothiazide, enalapril, amlodipine and spironolactone). Participants who achieve optimal blood pressure control may have visits spaced out if recommended by the nursing supervisor.

[figure not shown]
Figure 3. Intervention 1: CBPM Care Model.

iii. Intervention 2: Enhanced Community Blood Pressure Monitor-based with mobile health blood pressure monitoring model (eCBPM+) (Figure 4)

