Participants in the (eCBPM+) Arm will also be given a home BP cuff, but in this case these cuffs will include cellular network capability (Blipcare model), such that BP data can be directly transmitted to the electronic platform to allow nursing supervisor review. Similar to the standard CBPM arm, they will also be given training on its operation and assigned a CHW from the study team. Participants in this arm will be instructed to take daily BP measurements, which will be automatically uploaded onto the server to be made available by the nurse supervisors. CBPMs will return to participant homes every 2-4 weeks to ensure functionality of the devices and transmission, collect BP measurements if the system is not functional, assess for symptoms, and discuss treatment adherence and lifestyle recommendations. Nursing supervisors at the clinic will use the remotely collected BP data to initiate and tailor medications guided by the same standardized clinical decision support (CDS) algorithm, based on SA DoH hypertension control guidelines. Treatment decisions will be made by the nursing supervisors. Participants will either obtain medication(s) at the pharmacy or, as possible, have them delivered by a CBPM. As per the SOC arm, medications used will include those on the South African Essential Drug list and which are available in the clinic pharmacy (include hydrochlorothiazide, enalapril, amlodipine and atenolol). Participants who achieve optimal blood pressure control may have visits spaced out if recommended by the nursing supervisor.

Figure 4. Intervention 2: eCBPM+ Care Model.

b. Study Visit Schedule

i. Visit 1: Enrollment

At Study Visit 1, participants will complete the baseline questionnaire to collect sociodemographic, clinical and treatment history, self-reported medication adherence, quality of life, and resource allocation data (Table 1). Enrollment BP measurements will be collected by study nurses (independently from the CHW program) using standard BP measuring devices (OMRON model). Three measurements will be taken from the seated position with five minutes between each measure [14]. As described during the recruitment phase, all participants will receive a point of care (POC) creatinine (Abbott/Piccolo Xpress) to determine both eligibility and to guide BP regimen selection. Study staff will also review participant clinic records to collect data on clinic treatment history and blood pressure measurements in the past.

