One risk to participation is breach of confidentiality. Study staff will be trained in confidentiality and all staff members will be required to sign confidentiality agreements. Assurance of privacy in testing and communication of results will be done. Quality assurance processes will include regular support/supervision visits in the field and self-evaluations in this study. To ensure confidentiality of participants, all data will be coded by subject number. Data recorded on paper will be kept in locked cabinets with access only by members of the research team. There will be strict limited access to electronically stored data as well, using password protection. Research records will be kept confidential following national regulations. The subject's name or other personal identifiers will not be included with specimens sent to the laboratory, which will be identified only by a code number. Interviewers and support staff will be trained on procedures for maintaining confidentiality.

We will conduct a single specimen collection during this study to conduct point of care creatinine testing that will be administered by trained study staff. A trained nurse will collect blood from a pin prick using standard precautions requiring a few drops of blood (< 1ml) to be drawn.

Study participants in both the SOC and intervention arms with uncontrolled hypertension will receive one of four blood pressure medications on the South African Essential Medication list according to the local guidelines including: hydrochlorothiazide, enalapril or other angiotensin converting enzyme inhibitor, amlodipine, or a beta-blocker. No experimental medications will be used. Participants will be followed for side-effects in accordance with the South African hypertension guidelines by the nurses and the CBPMs. All participants who experience any adverse event will receive follow-up until adverse event is resolved by the local study staff. Severe and serious adverse events will

be documented and reported to the involved regulatory bodies per their regulations. A secondary risk of participation in this Aim is loss of time from participation in interviews and/or discomfort with the questions asked or nature of the conversations. All participation will be voluntary and participants will be free to pause, interrupt, or not respond to any questions or content areas that make them uncomfortable.

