Study recruitment will occur at the Nkundusi and Madwaleni primary health care clinics (PHC) in the AHRI Health and Demographic Surveillance Site (HDSS). All adults who present to these clinics during weekdays will be screened for potential enrolment.

Individuals are eligible to enrol if they:

- Are age ≥ 18 years old
- currently reside in the catchment area of the enrolment clinics with plans to remain in the area for the next 2 years
- have elevated blood pressure (systolic blood pressure >140 mm Hg or diastolic blood pressure >90 mmHg) at screening
- have evidence of at least one previous elevated blood pressure reading in the medical chart 6 months ago or earlier, to meet criteria for hypertension in the South African Department of Health guidelines which require elevated readings on at least two occasions.

Exclusion criteria are

- pregnant women, confirmed by urine β -HCG testing on the day of screening for women aged <55 years, or breastfeeding women
- symptomatic hypertension and a blood pressure >180 mm Hg systolic or 110 mmHg diastolic
- advanced chronic kidney disease (GFR <60 ml/min/1.73m²) as determined by point-of-care creatinine testing
- individuals on three or more anti-hypertensive medications at full dose

4. Randomisation

After informed consent, individuals will be randomised in blocks of 9 to one of the three study arms using the REDCap randomization module. Randomisation will be stratified by the clinic and active use of anti-hypertensive therapy at the time of enrolment.

5. Data collection

At enrolment, participants will be asked about sociodemographic characteristics, medical history and hypertension treatment history, self-reported medication adherence, quality of life, and resource allocation data to enable cost effectiveness analyses.

All participants will be followed up at 6 and 12 months after enrolment, where blood pressure will be measured by study nurses using a standardised Omron BP cuff. Blood pressure will be measured after the participant has been seated for 5 minutes. Three measurements will be taken on the same arm in the seated position, with each measurement taken 5 minutes apart. Data will also be collected on medication regimen changes and adherence, medical history including complications, hospitalizations and treatment side effects, and resource allocation, to enable estimates of program sustainability and longer term costs.

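### SAP 9.3 tabulates adverse events by arm without saying how they were found, although scheduled symptom enquiry differs by arm, so the table may partly reflect contact frequency.

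*SAP*

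**What the plan says.** **The table.** SAP 9.3 counts participants with any AE and adds that "the total number of AEs, will be tabulated by the treatment arm". AEs are also broken down by diagnosis, severity and relationship to the intervention. No test, odds ratio or confidence interval is planned for AEs, and no source of events is named.

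**Contact in the intervention arms.** For CBPM, Protocol V.G.a.ii says "CBPMs will return to participant homes every 2-4 weeks, or as guided by the clinic nurse", and at those visits they "assess for symptoms, and discuss treatment adherence and lifestyle recommendations". For eCBPM+, V.G.a.iii says "CBPMs will return to participant homes every 2-4 weeks to ensure functionality of the devices and transmission", again with symptom assessment. The interval is not fixed: "Participants who achieve optimal blood pressure control may have visits spaced out if recommended by the nursing supervisor". The protocol's introductory section says that CBPMs are employed to carry out study activities.

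**Contact in SOC.** Protocol V.G.a.i plans clinic visits at an unstated interval until control, then six-monthly. Symptoms, including those related to medication, are assessed at each visit. CBPMs may also do some monitoring, for adherence and education.

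**How AEs are identified.** Protocol V.I.b.ii names two routes, neither restricted by arm: clinical review by study staff at study visits, and participants reporting to their research assistant. Protocol V.M.a adds: "Participants will be followed for side-effects in accordance with the South African hypertension guidelines by the nurses and the CBPMs". SAP 5 has all arms seen at 6 and 12 months, with data collected on "medical history including complications, hospitalizations and treatment side effects".

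**Use of the data.** Under Protocol V.I.b.i the DSMB reviews safety by arm, including adverse events. Allocation is open to participants and clinic staff (V.F).

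**The concern.** A count of AEs depends on how often events occur and on how often someone asks. By design, the second differs between arms here. If events noticed at CBPM home visits are entered as AEs, or if repeated questioning prompts participants to report more, equal true rates would look like an excess in the intervention arms. A truly lower rate there could also be hidden.

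The intervention arms may also receive more drug treatment, which could raise true reaction rates. With sources pooled, a higher count could mean more treatment, more harm or more asking, and nothing in SAP 9.3 separates these. Adverse drug reactions are one of only two Aim 2 safety measures (Protocol V.K.c, SAP 2), and the DSMB looks at adverse events by arm.

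**Working it through.** The plan gives no AE rate, detection rate or safety sample size, so there is no figure of its own to reproduce. The check has three parts.

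**1. Scheduled contacts, from Protocol V.G.a and SAP 5**

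| | CBPM and eCBPM+ | SOC |
|---|---|---|
| Home visits with symptom assessment, 26 weeks | 26/4 = 6.5 to 26/2 = 13, if not spaced out | none scheduled; optional CBPM monitoring |
| Same, 52 weeks | 52/4 = 13 to 52/2 = 26, if not spaced out | none scheduled; optional CBPM monitoring |
| Clinic visits with symptom assessment | not specified | planned, but number cannot be computed |
| Study visits after enrolment | 1 by month 6, 2 by month 12 | 1 by month 6, 2 by month 12 |

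Only the last row is the same in every arm by design.

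**2. Do events found by CBPMs reach the table?** Protocol V.I.b.ii does not list CBPM visits as an AE source. V.M.a gives CBPMs a role in following side-effects and soon afterwards describes follow-up of adverse events by study staff, which makes entry plausible. SAP 9.3 is silent. The documents leave the question open.

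**3. What it would do if they did.** Let the true risk p be equal in all arms. Let c be the chance that an event is detected through routes common to all arms, and e the chance that CBPM contact picks up an event those routes missed. All three are assumptions.

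- Recorded risk in SOC: p × c
- Recorded risk in an intervention arm: p × [1 − (1 − c)(1 − e)]
- Apparent risk ratio: [1 − (1 − c)(1 − e)] / c, which does not depend on p

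| | e = 0 | e = 0.25 | e = 0.5 |
|---|---|---|---|
| c = 0.5 | 1.00 | 0.625/0.5 = 1.25 | 0.75/0.5 = 1.50 |
| c = 0.7 | 1.00 | 0.775/0.7 = 1.11 | 0.85/0.7 = 1.21 |
| c = 0.9 | 1.00 | 0.925/0.9 = 1.03 | 0.95/0.9 = 1.06 |

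With p = 10%, c = 0.5, e = 0.5 and the planned 258 per arm, SOC would record 258 × 0.10 × 0.5 = 12.9 participants with an event and an intervention arm 258 × 0.10 × 0.75 = 19.4. More extreme inputs give more: detection of 90% against 50% gives 0.9/0.5 = 1.8. The e = 0 column is what a comparison restricted to common routes would give, provided that CBPM contact does not change what participants report there.

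**The case against.** The strongest reply is that the protocol's AE section already defines identification through routes open to every arm, and CBPM visits are not among them. If the AE data come only from those routes, no event found by a CBPM enters the table directly and the ratio is 1.0. The V.M.a sentence about nurses and CBPMs stands in a paragraph covering SOC and intervention participants alike, so it does not itself show unequal follow-up. SOC participants have symptom checks at each clinic visit and may also see a CBPM. The AE table is descriptive and already split by severity, so severe events, which depend less on questioning, can be read separately.

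All of this stands, and it rules out stronger readings. A reader might infer that the table is shown to measure how often people were asked, that SOC has no symptom checks before month 6, or that the DSMB's recommendation will be distorted. The documents support none of these. The detection rates are invented, the number of SOC checks is unknown rather than zero, and any effect on the DSMB is conjecture.

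The reply does not remove the point. A route open to all arms need not yield equally: self-report can be prompted by repeated questioning, and allocation is open. A by-arm AE table will be read as a comparison whether or not it carries a test. SAP 9.3 also leaves the event set unclear. The stated measure is adverse drug reactions, 9.3 tabulates AEs, and V.I.b.ii requires logging only of unanticipated or severe events. Whether mild, expected reactions are counted cannot be told.

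**Conclusion.** The point holds as a gap in specification with a possible bias. Scheduled symptom enquiry differs by arm, and SAP 9.3 neither names nor separates the sources of its events. Whether that distorts the table depends on two things the documents do not settle: whether events found by CBPMs enter the AE data, and whether CBPM contact changes reporting through the common routes.

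Under equal true risk, the assumed detection rates give apparent ratios from 1.0 (no distortion) to about 1.5, or more with extreme inputs. These illustrate the mechanism and do not estimate its size. The point does not touch the blood pressure outcomes. It merits a change because a more comparable safety comparison can be made from data the plan already collects.

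**What to change.** In SAP 9.3:

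- State which events are tabulated (all AEs, drug reactions, or the logged unanticipated and severe events) and from which sources.
- Make the main by-arm comparison of non-serious AEs and drug reactions the events elicited by study nurses at the 6- and 12-month visits, using the same questions in all arms.
- Report deaths, hospitalisations and other serious events from all sources.
- Keep the all-source table as supplementary, split into study visit, CBPM visit, clinic and self-report where the record allows.
- Give the DSMB the same split.

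**Cost.** One more table and some SAP wording; the visit data are already planned. A source field may be missing for earlier events, since the protocol's change log lists changes during or after the trial from January 2023 and the SAP is dated October 2023. The visit-based table does not need that field.

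**Downsides.** Recall over six months under-counts mild events, and perhaps not equally, because people questioned often may remember more. Those who miss visits contribute no non-serious events to the main comparison. At the planned 20% loss that is 258 × 0.20 = 51.6, about 52 per arm. The supplementary table covers part of this loss.

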For participants who cannot be reached to schedule 6 or 12 month visits, a study staff member will attempt a home visit to collect outcome data.

6. Sample size

Based on patient attendance data from the two PHCs in our study in 2020, we estimate that there are over 1000 individuals with uncontrolled hypertension and thus eligible to enrol in the trial. We anticipate mean blood pressure at baseline will be 150/95 mmHg, with a standard deviation (SD) of 19 mmHg, based on previous studies. With 774 participants enrolled (258 per arm), we will have 80% power to detect a 5 mmHg difference between arms in the change of blood pressure from baseline to 6 months, assuming 20% loss to follow-up, a correlation between baseline and follow-up measurements of 0.5, and an alpha of 2.5% to account for multiple testing with comparisons between the SOC and both intervention arms (Table 1).

This same sample size will also give us greater than 80% power to detect an increase in the proportion of participants who achieve BP control (defined by a systolic BP <140 mmHg and diastolic BP <90mm Hg) at 6 months from 30% in the SOC arm to 45% in the interventions arms, or from 40% in the SOC to 56% in the intervention, also allowing for an alpha of 2.5% to account for multiple testing.

Table 1. Differences in change from baseline that can be detected with 80% power

N enrolled per arm	Loss to follow-up	Difference that can be detected (mmHg)	Standard deviation	Correlation between observations	Power
330	20%	5.0	19.0	0.20	80%
258	20%	5.0	19.0	0.50	80%
148	20%	7.5	19.0	0.20	80%
115	20%	7.5	19.0	0.50	80%

7. Definitions and analysis populations

All analyses will be conducted using the intention-to-treat principle, where all randomised participants will be included in the analysis regardless of adherence to the intervention.

All analyses of blood pressure will use the average of the second and third measurement as the blood pressure measurement for that visit. In the primary analyses, participants who are missing any of the three measurements will be considered to be missing blood pressure data for that visit. As a sensitivity analysis, individuals with fewer than three measurements will be included, using the average if there are two, or a single measurement if only one is available.

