9.1 Primary objective

The primary objective of the trial is to examine the effect of the interventions on the change from baseline in systolic blood pressure 6 months after enrolment. The mean

and SD systolic blood pressure, and the mean and SD change from baseline, at the 6 and 12 month visits will be summarised by treatment arm.

Linear regression will be used to estimate the mean difference, and its 95% confidence interval (CI), between each intervention and SOC (i.e. CBPM vs SOC and eCBPM+ vs. SOC) in the change from baseline at 6 months. The response variable will be systolic blood pressure at 6 months; the model will include treatment arm, clinic, active use of hypertension medication and baseline systolic blood pressure.

In secondary exploratory analyses, we will adjust for baseline values of age, sex, body mass index (BMI), smoking status and HIV. In separate models, we will fit an interaction term between the treatment arm and sub-groups of interest (e.g. sex, age group, co-morbidities) to examine sub-group effect sizes and potential effect modification.

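### The exploratory 12-month SBP mixed model states no residual structure; read in the usual way it pools variance over visits, so its visit-specific intervals are miscalibrated if variance differs between 6 and 12 months

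*SAP*

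**What the plan says.** SAP section 10, headed "Additional exploratory analyses", describes a linear mixed model for SBP at 6 and 12 months. Of its fixed effects it says "the model will include fixed effects for treatment arm, visit, a treatment arm-visit interaction term, randomisation strata", and it then adds baseline SBP as a single term. The only statement about the within-participant structure is "participant as a random effect to account for correlation of repeated measurements within the participant". A residual covariance, visit-specific variances, robust standard errors and a baseline-by-visit term are not mentioned.

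The interaction lets the effect differ between visits. If it does not reach p<0.10, the plan says "we will drop it from the model and estimate the overall effect of each intervention (vs SOC) on the change in systolic blood pressure". The section also states: "Estimates from random effects models are valid under the assumption that the outcome data are missing at random", conditional on the observed outcomes and covariates.

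The primary analysis in SAP section 9.1 is a separate regression: "The response variable will be systolic blood pressure at 6 months; the model will include treatment arm, clinic, active use of hypertension medication", plus baseline SBP. For 12-month SBP, section 9.1 plans only means and SDs by arm.

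**The concern.** With two follow-up visits, a random intercept and one residual variance give both visits the same variance. The model then lets the effect change over time but not its precision. A standard error built on the average variance is too small at the more variable visit and too large at the other.

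This is the only model in the SAP that gives a between-arm SBP comparison specific to 12 months. At stake is whether that exploratory interval has its nominal coverage when it is reported.

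**Working it through.** **Inputs.** SAP section 6 gives an SD of 19 mmHg, 258 enrolled per arm, 20% loss and "a correlation between baseline and follow-up measurements of 0.5". It gives no SD or correlation for 12 months, so those are assumed below. SAP section 10 states no interval level; 95% is assumed, as in section 9.1.

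**The plan's own figure.** The baseline-adjusted variance is 19² × (1 − 0.5²) = 270.75. With two-sided alpha 0.025 and 80% power, n = 2 × (2.2414 + 0.8416)² × 270.75 / 5² = 205.9, so 206 per arm; 206 / 0.8 = 257.5, so 258. This matches the plan. The other three rows of SAP Table 1 reproduce in the same way.

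**Formulas (complete data, 206 per arm, interaction kept in the model).** Let b6 = r6 × SD6 / 19 and b12 = r12 × SD12 / 19 be the baseline slopes. The fitted common slope is their mean, b.

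- Residual variance at visit k: Vk = SDk² × (1 − rk²) + (bk − b)² × 19²
- Variance used by the model at both visits: Vm = (V6 + V12) / 2
- Model SE / true SE at 12 months: √(Vm / V12)
- Coverage: 2Φ(1.96 × ratio) − 1
- Half-width: 1.96 × √(2V / 206)

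**Example.** Hold 6 months at SD 19, r 0.5, and let r fall to 0.4 at 12 months with SD 19. Then b = 0.45, V6 = 270.75 + 0.90 = 271.65, V12 = 361 × 0.84 + 0.90 = 304.14 and Vm = 287.90. The ratio is √(287.90 / 304.14) = 0.973.

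| Assumed 12-month SD, r | V6 | V12 | SE ratio, 12 m | Coverage, 12 m | Coverage, 6 m | 12 m half-width, model / true (mmHg) |
|---|---|---|---|---|---|---|
| 19, 0.5 | 270.75 | 270.75 | 1.000 | 95.0% | 95.0% | 3.18 / 3.18 |
| 19, 0.4 | 271.65 | 304.14 | 0.973 | 94.4% | 95.6% | 3.28 / 3.37 |
| 19, 0.2 | 278.87 | 354.68 | 0.945 | 93.6% | 96.3% | 3.44 / 3.64 |
| 22, 0.5 | 271.31 | 363.56 | 0.934 | 93.3% | 96.6% | 3.44 / 3.68 |
| 22, 0.3 | 272.85 | 442.54 | 0.899 | 92.2% | 97.5% | 3.65 / 4.06 |
| 17, 0.5 | 271.00 | 217.00 | 1.060 | 96.2% | 93.7% | 3.02 / 2.84 |

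A more extreme assumption, SD 24 and r 0.3, gives a ratio of 0.871 and coverage of 91.2%.

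**Simulation.** REML fits with 258 per arm, about 19-21% missing per visit, an assumed residual correlation of 0.4 and 2,000 runs per scenario (Monte Carlo SE about √(0.95 × 0.05 / 2000) = 0.5 points) gave these 12-month coverages:

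| Assumed 12-month SD, r | SAP model | Unstructured covariance + baseline by visit |
|---|---|---|
| 19, 0.5 | 94.9% | 94.8% |
| 19, 0.3 | 94.3% | 95.7% |
| 22, 0.5 | 93.3% | 95.2% |
| 22, 0.3 | 92.6% | 95.6% |

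**Is the single slope to blame?** With residual variance held equal and only the slope falling from 0.5 to 0.2, the SE ratio was 0.981, against 0.980 with no change, and coverage was 94.4%. The single slope does not narrow the interval. Visit-specific adjustment lowered the empirical 12-month SE from 1.674 to 1.648, about 1.6%.

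**Interaction and overall effect.** Let C be the residual covariance between visits. The model variance of the 12-minus-6-month contrast is proportional to 2Vm − 2C = V6 + V12 − 2C, which is the true value. For the average of the two visits it is (2Vm + 2C) / 4 = (V6 + V12 + 2C) / 4, again the true value. With 20% missing per visit (4,000 runs), coverage was 94.6-95.5% for the interaction and 94.8-95.5% for the overall effect.

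**The case against.** The strongest reply is that this is a conventional model in an exploratory section, and that most of what it delivers is sound. The interaction test and the pooled effect keep their nominal properties. Only the visit-specific contrasts are exposed, and they matter only when the interaction is kept. In the mildest case the loss is about half a percentage point of coverage. All of that stands.

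A reader might infer more than the documents support:

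- *The SAP imposes equal variance.* It is silent on residual structure. Equal variance is the usual reading of a participant random effect, not a stated choice.
- *SAP Table 1 shows correlation falling over time.* Its values of 0.2 and 0.5 are alternative planning assumptions for the 6-month sample size and say nothing about 12 months.
- *The 12-month interval will be too narrow.* That depends on the direction of change. If SBP becomes less variable, the interval is too wide.
- *The single baseline term causes the narrowing.* The check above shows that it does not. A falling correlation matters at constant SD because it raises the 12-month residual variance.
- *The trial's evidence on durability is undermined.* The interaction test is unaffected, section 9.1 reports 12-month means and SDs, and SAP section 2 leaves sustainability to a separate analysis plan. Protocol Table 4 lists SBP change from 6 to 12 months among the sustainability measures.
- *The missing-at-random statement fails.* Likelihood inference under that assumption does also need an adequate covariance, but no bias has been shown here.

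**Conclusion.** The point holds as a small one. On the usual reading, the visit-specific intervals in the SAP section 10 SBP model are correct only if residual variance is equal at 6 and 12 months, and the plan neither states nor supports that condition. If variance rises or correlation with baseline falls by 12 months, the 12-month SE is about 3-10% too small, with coverage about 92-94.5%, and the 6-month interval from this model is too wide. At SD 22 and r 0.3 the half-width is understated by 4.06 − 3.65 = 0.41 mmHg. If variance falls, the errors reverse.

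These sizes rest on assumed 12-month SDs up to 22 and correlations down to 0.2, with 6 months held at the plan's SD 19 and r 0.5. They apply to the contrast as fitted, without conditioning on the interaction passing p<0.10. The 6-month primary result comes from its own regression and does not change.

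**What to change.** In SAP section 10, replace the participant random intercept in the SBP model with an unstructured 2x2 within-participant covariance, fitted by REML. This is the part that corrects the visit-specific intervals, in whichever direction the variance moves. Also add a baseline SBP by visit term so that baseline adjustment is specific to each visit; its benefit is a minor gain in precision. The other fixed effects stay as listed.

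The cost is one sentence in the SAP and two more parameters, with about 774 × 0.8 = 619 participants expected at follow-up. In the simulation with no change in variance, coverage was 94.8% against 94.9% for the SAP model, so nothing material is lost if the equal-variance assumption turns out to be right.
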